7.4.9. Clinical Safety Laboratory Assessments

All protocol required laboratory assessments, as defined in Table 2, must be conducted in accordance with the Central Laboratory Manual, and Protocol Time and Events Schedule (Section 7.1). Laboratory requisition forms must be completed and samples must be clearly labelled with the subject number, protocol number, site/centre number, and visit date. Details for the preparation and shipment of samples will be provided by the laboratory and are detailed in the central laboratory manual. Reference ranges for all safety parameters will be provided to the site by the laboratory responsible for the assessments.

All study-required laboratory assessments will be performed by a central laboratory.

If additional non-protocol specified laboratory assessments are performed at the institution's local laboratory and result in a change in subject management or are considered clinically significant by the investigator (e.g., SAE or AE or dose modification) the results must be recorded in the eCRF.

Refer to the Central Laboratory Manual for appropriate processing and handling of samples to avoid duplicate and/or additional blood draws.

Haematology, clinical chemistry, urinalysis and additional parameters to be tested are listed in [Table 2](#).

Table 2 Protocol Required Safety Laboratory Assessments

| Laboratory Assessments | Parameters | | | |
|---------------------------------|--|---------------------|-------------------------------------|----------------------------|
| Haematology | Platelet Count | RBC Indices: | WBC count with Differential: | |
| | RBC Count | MCV | Neutrophils | |
| | Hemoglobin | MCH | Lymphocytes | |
| | Hematocrit | | Monocytes | |
| | | | Eosinophils | |
| | | | Basophils | |
| Clinical Chemistry ¹ | BUN | Potassium | AST (SGOT) | Total and direct bilirubin |
| | Creatinine | Sodium | ALT (SGPT) | Total Protein |
| | Glucose | Calcium | Alkaline phosphatase | Albumin |
| Routine Urinalysis | 
 Specific gravity pH, glucose, protein, blood and ketones by dipstick Microscopic examination (if blood or protein is abnormal) Urine pregnancy | | | |
| Other Screening Tests | 
 HIV Hepatitis B surface antigen (HBsAg) Hepatitis B core antibody (HBcAb) Hepatitis C (Hep C antibody) Diagnostic TB test: either QuantiFERON Gold test or T-spot test FSH and estradiol (as needed in women of non-child bearing potential only) Alcohol and drug screen (to include at minimum: amphetamines, barbiturates, cocaine, opiates, cannabinoids and benzodiazepines) Serum hCG Pregnancy test (as needed for women of child bearing potential)² | | | |
| NOTES : | 
 Details of Liver Chemistry Stopping Criteria and Required Actions and Follow-Up Assessments after liver stopping or monitoring event are given in Section 5.4.1 and Appendix 2. Local urine testing will be standard for the protocol unless serum testing is required by local regulation or ethics committee. | | | |

All laboratory tests with values that are considered clinically significantly abnormal during participation in the study or within 12 weeks after the last dose of study treatment should be repeated until the values return to normal or baseline. If such values do not return to normal within a period judged reasonable by the investigator, the etiology should be identified and the sponsor notified.

7.5. Pharmacokinetics

7.5.1. Blood Sample Collection

Blood samples for pharmacokinetic (PK) analysis of GSK3196165 will be collected at the time points indicated in Section 7.1, Time and Events Table. The actual date and time of each blood sample collection will be recorded. The timing of PK samples may be altered and/or PK samples may be obtained at additional time points to ensure thorough PK monitoring.

Collection, processing, storage and shipping procedures are provided in the Central Laboratory Manual.

7.5.2. Sample Analysis

Serum analysis will be performed under the control of PTS-DMPK/Scinovo, GlaxoSmithKline, the details of which will be included in the Central Laboratory Manual. Concentrations of GSK3196165 will be determined in serum samples using the currently approved bioanalytical methodology. Raw data will be archived at the bioanalytical site (detailed in the Central Laboratory Manual).

7.6. Biomarkers and Imaging

7.6.1. Magnetic Resonance Imaging

Each subject's affected hand (corresponding to the affected hand which is determined and documented at screening) will be imaged by MRI at screening, week 12 and week 22 (see Section 7.1). If a scanning failure occurs at any visit, if feasible a rescan is allowed within 10 days of the failed scan *after* consultation and agreement with the GSK medical monitor. There will be a minimum of 24 hours between scans where gadolinium contrast is used and any rescan will follow local imaging site regulations for repeat gadolinium administration. The MRI will be used in order to non-invasively quantify the degree of inflammation and structural changes within the target joint.

Each MRI total scan time should not exceed 1 hour. For each subject, MRIs must be performed on the same scanner and using the same type of chelated gadolinium contrast agent as was used at screening. If scanning cannot occur on the same scanner within the visit time window due to hardware failure, an alternate scanner may be used or the time window may be extended by 3 days only *after* consultation and agreement with the GSK medical monitor.

On attendance at the MRI department, subjects will be placed in the scanner and will be prepared for intravenous contrast agent administration. The scanning protocol will

include routine localisers, T1 measurement sequences, dynamic DCE-MRI acquisition, structural scans for bone shape analysis, and acquisitions required for OMERACT HOAMRIS and RAMRIQ scoring. Additional exploratory MRI endpoints, as detailed in the Acquisition Manual, may also be acquired for exploratory purposes.

Details of scanning site training procedures, acceptable gadolinium contrast agents, and scanning protocols will be provided in a dedicated Imaging Manual.

All MRI scans will be reported at the site by a radiologist (non-anonymised) for clinical abnormalities.

7.6.2. Novel Biomarkers

With the subject's consent, blood samples will be collected during this study and may be used for the purposes of measuring novel biomarkers to identify factors that may influence osteoarthritis disease severity and progression, and/or medically related conditions, as well as the biological and clinical responses to GSK3196165. If relevant, this approach will be extended to include the identification of biomarkers associated with adverse events.

Blood samples for novel biomarkers will be collected at the time points indicated in Section 7.1 and processed to plasma (as summarised below). The timing of the collections may be adjusted on the basis of emerging pharmacokinetic or pharmacodynamic (PD) data from this study or other new information in order to ensure optimal evaluation of the PD endpoints.

Collection, processing, storage and shipping procedures are provided in the Central Laboratory Manual.

Novel candidate biomarkers and subsequently discovered biomarkers of the biological response associated with osteoarthritis or medically related conditions and/or the action of GSK3196165 may be identified by application of techniques including, but not limited to:

- Biochemical analysis.
- Proteome analysis.
- Metabolomic analysis.

All samples will be retained for a maximum of 15 years after the last subject completes the trial.

The results of these biomarker investigations and other exploratory endpoints, may be reported separately from the main study report. This will be detailed in the reporting and analysis plan (RAP).

7.7. Genetics

Information regarding genetic research is included in [Appendix 3](#).

7.8. Value Evidence and Outcomes

7.8.1. Post-treatment Interviews

Post-treatment interviews will be conducted as shown in the Time and Events Table (Section 7.1) to explore subjects' experience with study treatment. Post-treatment interviews are qualitative interviews conducted with study subjects to capture subject experiences in drug development on completion of participation in a clinical study. Interview questions designed to fully assess a subject's experience with a study medication are administered in a semi-structured format by a trained interviewer. Subject feedback will be captured in a data collection sheet as well as being audio-taped for subsequent transcription and qualitative analysis. The interview technique and questions are described in [Appendix 12](#) and training as well as training material references will be provided to site personnel who will administer the interviews.

8. DATA MANAGEMENT

- For this study subject data will be entered into GSK defined CRFs, transmitted electronically to GSK or designee and combined with data provided from other sources in a validated data system.
- Management of clinical data will be performed in accordance with applicable GSK standards and data cleaning procedures to ensure the integrity of the data, e.g., removing errors and inconsistencies in the data.
- Adverse events and concomitant medications terms will be coded using MedDRA (Medical Dictionary for Regulatory Activities) and an internal validated medication dictionary, GSKDrug.
- eCRFs (including queries and audit trails) will be retained by GSK, and copies will be sent to the investigator to maintain as the investigator copy. Subject initials will not be collected or transmitted to GSK according to GSK policy.
- For this study subject data will be collected in electronic GSK defined case report forms (eCRF). For the PRO component, the data will be collected and managed on the modality as determined prior to the start of the study.

9. STATISTICAL CONSIDERATIONS AND DATA ANALYSES

9.1. Hypotheses

The primary endpoint of the study is to evaluate the change from baseline in 24h average hand pain intensity at Week 6, as measured by daily pain Numerical Rating Scale (NRS) (see [Appendix 8](#)) averaged over the 7 days prior to assessment visit with GSK3196165 or placebo in adult subjects with HOA.

The study will test the null hypothesis that there is no difference between GSK3196165 and placebo in the change from baseline in the 24h average Pain NRS at Week 6. The alternative hypothesis is there is a difference between GSK3196165 and placebo in the change from baseline in the 24h average Pain NRS at Week 6 using a two-sided test.

9.2. Sample Size Considerations

9.2.1. Sample Size Assumptions

Using a t-test, a sample size of 20 subjects per arm will detect a minimal significant difference over placebo of approximately 2 points in the change from baseline in the 24h average Pain NRS at Week 6 of the 12 week treatment period and has approximately 80% power to detect a difference of 2.7 points assuming an SD = 3 and a 5% significance level. The estimate of variability is based on sample size assumptions from a literature review of two studies in knee OA using a pain NRS [Steigerwald; 2012, Afilalo; 2010].

9.2.2. Sample Size Sensitivity

The power of the study will be affected by changes from the assumed estimate of the SD and [Table 3](#) shows the effect on power and the minimally significant difference under varying estimates of the SD, and the number of subjects needed for 80% power.

Table 3 Power to Detect a Difference -2.7 points for Change from baseline in 24h average Pain NRS at 6 Weeks under Varying Estimates of the SD

| SD Estimate | Power with 20 Subjects / arm | Minimal Significant Difference with 20 subjects / arm | N / arm for 80% power |
|-------------|------------------------------|---|-----------------------|
| 2.5 | 91% | -1.6 | 15 |
| 3 | 80% | -2 | 20 |
| 3.5 | 66% | -2.2 | 28 |

9.2.3. Sample Size Re-estimation or Adjustment

No Sample size re-estimation is planned.

9.3. Data Analysis Considerations

9.3.1. Analysis Populations

Intent to Treat (ITT) population: The ITT population is defined as all subjects who were randomised to treatment and who received at least one dose of study treatment. This population will be based on the randomised treatment group.

Safety population: The safety population is defined as all subjects who receive at least one dose of study treatment. This population will be based on the actual treatment received.

Pharmacokinetic (PK) population: The PK population is defined as all subjects who are in the 'Safety' population and who have at least one valid PK assessment.

9.3.2. Interim Analysis

An interim analysis will be performed during the study to review the available PK data and target engagement biomarkers. The timing of this analysis will coincide with other

internal decision making across the GSK3196165 project. Unblinded data will be shared with members of Clinical Pharmacology Modelling and Simulation (CPMS), Clinical Statistics and GSK study team members who have no involvement in the acquisition of the data or direct contact with sites. No other members of the GSK study team will be unblinded to this data.

Another formal interim analysis may be conducted on the key safety, primary efficacy and key secondary endpoints in this study. The purpose of this interim will be to help with decision-making regarding the subsequent clinical development of GSK3196165 for OA. The timing of this analysis will be once a minimum of 30 subjects have completed day 43 (Week 6). Full details will be provided in the RAP which will be available prior to the data being unblinded. Unblinded data will only be shared with selected members of the GSK study team. No members of the GSK study team who have involvement in the acquisition of the data or who have direct contact with the sites will be unblinded to this data.

Recruitment will continue while the interim analyses are being conducted.

For both interim analyses, unblinded summary level data will be available and if required anonymised individual data will be available on request. Only the study pharmacokineticist or study statistician generating the interim analysis results will be unblinded to individual subject treatment allocations.

9.4. Key Elements of Analysis Plan

Full details of all analyses will be provided in the RAP.

9.4.1. Primary Analyses

The primary endpoint will be analysed using a repeated measures model (MMRM) adjusted for baseline pain score, treatment group, visit and the visit by treatment group interaction as fixed effects, patient as a random effect and day within patient as a repeated effect, using an unstructured covariance matrix. The point estimates and corresponding 95% confidence intervals for the treatment differences will be constructed, using the residual error from the repeated measures model. Least squares means and 95% confidence intervals over time for each treatment group will be plotted. Further sensitivity analyses will be conducted to assess the impact of missing data and non-parametric analyses may be conducted if the normality assumption does not hold.

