4.4. Type and Number of Subjects

Approximately 40 subjects with active inflammatory HOA who have passed all screening assessments, will be enrolled onto the study. At least 40 subjects will be randomized across the two treatment arms, to either placebo or GSK3196165, in a 1:1 ratio (n=20 per arm).

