9.4.2. Secondary Analyses

Continuous endpoints will be analysed using the same methods as the primary endpoint.

Binary endpoints, e.g. the proportion of subjects that achieve a 30% reduction in the Pain NRS score from baseline, will be summarised using counts and proportions in remission and analysed using a Generalised Estimating Equation (GEE) model comparing GSK3196165 with placebo at each time point. Subjects with missing Pain NRS scores will be considered as non-responders.

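### Does adding a patient random effect to an unstructured within-patient matrix damage the primary MMRM or its confidence interval?

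*Protocol*

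**What the plan says.** The primary endpoint is one value per patient per visit: the daily pain score "averaged over the 7 days prior to assessment visit", taken at Week 6 as a change from baseline (Protocol Section 9.1).

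Section 9.4.1 analyses it with an MMRM "adjusted for baseline pain score, treatment group, visit and the visit by treatment group interaction as fixed effects". The covariance part is "patient as a random effect and day within patient as a repeated effect, using an unstructured covariance matrix". The synopsis uses the same words. The 95% intervals for the treatment differences are to be built "using the residual error from the repeated measures model". Section 9.4.2 extends the model: "Continuous endpoints will be analysed using the same methods as the primary endpoint".

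Section 9.4 leaves the full analysis details to the Reporting and Analysis Plan (RAP). Section 6.4 requires the RAP to be approved before the first unblinding. The RAP is not at hand.

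**The concern.** An unstructured matrix R over a patient's visits already has a free parameter for every variance and covariance. A patient random intercept with variance c adds the same constant to all of them. Data inform only the sum, so c and R cannot be separated.

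Three consequences might follow:

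- Software could fail to converge, or could return an arbitrary split between patient and residual variance.
- The interval instruction could become ambiguous. If the residual error were taken as R alone, the interval for a comparison between different patients would leave out part of the between-patient variance and be too narrow.
- The repeated effect is named by day and the fixed time factor by visit, so it might be unclear whether daily diary scores or visit-level means enter the model.

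At stake would be the interval for the primary endpoint and, through Section 9.4.2, for every continuous secondary endpoint.

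**Working it through.** **Design figure first.** Inputs from Section 9.2.1: 20 per arm, SD 3, difference 2.7, two-sided 5%.

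- SE = 3 × sqrt(2/20) = 0.949.
- t(0.975, 38 df) = 2.024, so the half-width, which is also the minimal significant difference, is 2.024 × 0.949 = 1.92. The protocol says about 2.
- Power is 79.2% by the noncentral t and 81.2% by the normal approximation. The protocol says about 80%.

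The stated figures reproduce. They come from a t-test and do not involve the covariance parametrisation.

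**Redundancy.** With T visits the marginal covariance is V = R + cJ, where J is the all-ones matrix. R has T(T+1)/2 parameters and c adds one. J lies in the space that R already spans, so the rank stays at T(T+1)/2. The protocol does not list the visits in the model. Assuming Weeks 1, 2, 3, 4, 6, 8, 10 and 12 from the Time and Events table, T = 8 gives 37 parameters and rank 36. Adding Week 22 gives 46 and rank 45. The surplus is one parameter for any T.

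**What the redundancy leaves alone.** The fixed-effect estimates and their covariance, (sum of X'V⁻¹X)⁻¹, depend on R and c only through V. In a simulated trial (20 + 20 patients, eight visits, SD 3, assumed correlations), V was estimated by REML and then split at several values of c:

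| c | REML log-likelihood | Week 6 difference | SE from V | SE from R alone |
|---|---|---|---|---|
| 0 | -257.9985 | -3.303 | 0.781 | 0.781 |
| 0.82 | -257.9985 | -3.303 | 0.781 | 0.727 |
| 1.64 | -257.9985 | -3.303 | 0.781 | 0.668 |
| 2.46 | -257.9985 | -3.303 | 0.781 | 0.603 |
| 3.28 | -257.9985 | -3.303 | 0.781 | 0.531 |

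Only the last column moves, and it is not the standard error that the fitted model gives for the treatment contrast.

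**Convergence.** Re-evaluating a fixed V cannot show how a fit behaves. The model as written was therefore fitted by REML to two simulated 20 + 20 patient data sets from several starting values. It converged every time, with the same likelihood, Week 6 difference and SE as the model without the random effect (SEs 0.942 and 0.911). Only the patient/residual split depended on the starting value.

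**The narrow-interval reading.** If a share s of the variance were removed from the SE, the half-width would be 1.92 × sqrt(1 − s) and the coverage 2 × T38(2.024 × sqrt(1 − s)) − 1, where T38 is the t distribution function with 38 df. For s = 0.5 that is 1.36 and about 84%. The protocol gives no value for s, and the redundancy itself means that s cannot be estimated.

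**Day or visit.** Section 4.3 labels the dosing visits by study day (43, 57 and 71 for Weeks 6, 8 and 10). Section 7.1.3 calls the Week 12 procedures Day 85, and Section 9.3.2 equates day 43 with Week 6. A daily-diary reading over 84 days would need 84 × 85/2 = 3570 covariance parameters from about 40 patients, and it would contradict the 7-day-mean endpoint. Day is a visit label.

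**The case for a change.** The best case for a change is that this is a fault in stated text, not a missing detail. It stands in both the synopsis and Section 9.4.1, is carried to the secondary endpoints, and a RAP that follows the protocol would inherit it. In a model with both a patient effect and a residual, residual ordinarily means what remains after the patient effect, and here that part is not identified. The repair would take a few words and cost nothing.

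The algebra stands in full, and so does the remark that the sentence is loosely worded. The harm does not. The interval is attributed to the error of the repeated measures model, which most naturally means the error of the fitted model as a whole. Nothing in the protocol asks for between-patient variance to be taken out of a between-patient comparison, and standard mixed-model contrasts do not do so. The coverage loss needs both the less natural reading and an assumed variance share.

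Two simulated data sets do not prove that every program converges on every data set. If a fit did stall, dropping the redundant term would be the obvious step, and it would leave the estimate and its standard error as they are.

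**Conclusion.** The concern is right about the algebra, but no change follows. The phrase is best read as a loose description of an ordinary unstructured MMRM with patient as the subject. Whether or not the patient effect is kept, the Week 6 difference, its model-based standard error, the sample size and the power are the same. At SD 3 with 20 per arm the half-width is 1.92 points in a two-group approximation without baseline adjustment.

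This conclusion assumes that the intervals come from the treatment contrast of the full fitted model, which is the normal route, and that day means visit, as the protocol's own labelling indicates. The visit list and the simulation values are assumptions too, but the one-parameter redundancy and the invariance of the contrast do not depend on them. A statistician writing the RAP can tidy the wording without altering any result.

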9.4.2. Secondary Analyses

Continuous endpoints will be analysed using the same methods as the primary endpoint.

Binary endpoints, e.g. the proportion of subjects that achieve a 30% reduction in the Pain NRS score from baseline, will be summarised using counts and proportions in remission and analysed using a Generalised Estimating Equation (GEE) model comparing GSK3196165 with placebo at each time point. Subjects with missing Pain NRS scores will be considered as non-responders.

9.4.3. Other Analyses

All safety evaluations will be based on the Safety population. Clinical interpretation will be based upon review and displays of each safety parameter, including adverse events (AE), serious adverse events (SAE) and AEs of special interest. Analyses of AEs by the investigator reported relationship to investigational produce will also be performed.

Full details of all summaries and analyses will be included in the RAP.

10. STUDY GOVERNANCE CONSIDERATIONS

10.1. Posting of Information on Publicly Available Clinical Trial Registers

Study information from this protocol will be posted on publicly available clinical trial registers before enrolment of subjects begins.

